A Phase 1 Study of TPI 287 Concurrent with Fractionated Stereotactic Radiotherapy (FSRT) in Treatment of Brain Metastases from Advanced Breast and Non-Small Cell Lung (NSCL) Cancer

NCT02187822

Version 1.6

July 7, 2014

Title:A Phase 1 Study of TPI 287 Concurrent with Fractionated Stereotactic
Radiotherapy (FSRT) in Treatment of Brain Metastases from Advanced
Breast and Non-Small Cell Lung (NSCL) Cancer

Protocol Number: MCC 17816

- **IND Number:** 123010
- Sponsor:H. Lee Moffitt Cancer Center & Research Institute, Inc.
(Moffitt Cancer Center), Investigator Initiated Trial

Investigational Product: TPI 287

Principal Investigators:[name]
Department of Neuro-Oncology, Moffitt Cancer Center
[name]
[name]

Co-Investigators:

[name] [name] [name] [name] [name] [name] [name] [name], DO [name] [name], PhD

Statistician:

Original Protocol:

July 7th, 2014

PROTOCOL SYNOPSIS

TITLE	A Phase 1 Study of TPI 287 Concurrent with Fractionated Stereotactic Radiotherapy (FSRT) in Treatment of Brain Metastases from Advanced Breast and Non-Small Cell Lung (NSCL) Cancer	
STUDY PHASE	Ι	
PRIMARY	To evaluate the safety, tolerability, and to determine the maximum	
OBJECTIVES	tolerated dose (MTD) of TPI 287 given concurrently with fractionated stereotactic radiotherapy (FSRT) to treat brain metastases from advanced breast and non-small cell lung cancer.	
SECONDARY	To characterize the pharmacokinetics and anti-tumor effect of TPI 287	
OBJECTIVES	administered concurrently with FSRT in the treatment of patients with breast and NSCL cancers metastatic to the brain; and to evaluate the effect of treatment on measures of quality of life.	
HYPOTHESES	TPI 287, given concurrently with FSRT, will improve local control and decrease distant brain failure in patients with brain metastases from advanced breast and NSCL cancers.	
STUDY DESIGN	 Dose escalation phase: The MTD for TPI 287 given concurrently with FSRT will be determined using the standard 3+3 study design. Dose expansion phase: Patients will be treated with TPI 287 at MTD given concurrently with FSRT to further assess toxicity and tumor response. 	
PRIMARY	Primary endpoints:	
ENDPOINTS AND SECONDARY ENDPOINTS	 To determine the maximum tolerated dose (MTD) of TPI 287 given concurrently with FSRT to treat brain metastases from advanced breast and NSCL cancers and to determine the recommended phase 2 dose (RP2D) To determine the safety and toxicity of TPI 287 given concurrently with FSRT to treat brain metastases from advanced breast and NSCL cancers 	
	Secondary endpoints:	
	 To determine the local control rate To determine the distant intra-cranial control rate To determine the short-term (≤ 30 days post-treatment) and long-term (> 30 days post treatment) adverse effects To determine the PFS To evaluate the effect of concurrent therapy with TPI 287 and 	

	FSRT on measures of quality of life	
SAMPLE SIZE	The maximum number for the dose escalation phase will be 36 patients. In the dose expansion phase, a total of 10 patients (including patients treated at the MTD from dose escalation phase) will be enrolled to confirm the safety and to assess radiologic response.	
SUMMARY OF SUBJECT ELIGIBILITY	 Major inclusion criteria: Patients age 18 years and older with brain metastasis (up to 3 metastatic brain lesions) from histologically proven advanced breast and NSCL cancers which have not been treated with previous brain radiation. Maximum diameter of each brain lesion ≤ 5 cm and maximum tumor volume ≤ 120 cc Adequate organ function Systemic chemotherapy washout period ≥ 7 days. For investigational drugs and monoclonal antibodies washout period ≥ 5x drug half-life. ECOG ≤ 2 	
	 Major exclusion criteria: Previous treatment of the target lesions with radiation therapy Previous whole brain radiotherapy Pregnant and nursing women Patients who are unable to give informed consent 	
INVESTIGATIONAL TREATMENT	TPI 287 will be administered intravenously prior to treatment of brain metastasis with FSRT on day 1 and will be given for 2 more weekly doses.	

SCHEMA

Patients with advanced breast and NSCL cancers metastatic to brain not amenable to surgical resection or radiosurgery

TPI 287 concurrent with FSRT (25 Gy in 5 fractions) on day 1 Single agent TPI 287

on day 8, and day 15

Clinical and radiologic assessment every 3 months until the patient is off-study or reaches 18-month study completion date

Dose Escalation Phase

Dose Escalation Schedule	
Dose	
TPI 287 IV	Radiotherapy
7 mg/m ² /dose	5 Gy daily fraction
14 mg/m ² /dose	5 Gy daily fraction
28 mg/m ² /dose	5 Gy daily fraction
56 mg/m ² /dose	5 Gy daily fraction

1. OBJECTIVES

1.1 Phase 1 Primary Objectives

The primary objectives of this study are to evaluate the safety, tolerability, and to determine the maximum tolerated dose (MTD) of TPI 287 given concurrently with fractionated stereotactic radiotherapy (FSRT) to treat brain metastases from advanced breast and NSCL cancers.

1.2 Secondary Objectives

The secondary objectives are to characterize the pharmacokinetics and anti-tumor effect of TPI 287 administered concurrently with FSRT in the treatment of patients with breast and NSCL cancers metastatic to the brain; and to evaluate the effect of treatment on measures of quality of life.

2. BACKGROUND

2.1 Brain Metastases

Brain metastases are a grave complication of cancer. They exceed the number of primary brain tumours by at least four times and occur in about 25% of all cancer patients totalling approximately 170,000 new cases each year in the United States.^{1,2} Brain metastases may originate from lung (40–50%), breast (15–25%), melanoma (5–20%), and kidney (5–10%) primary sites.² Moreover, there is evidence that the overall incidence of brain metastases is increasing as a result of improvements in systemic treatments. While these treatments increase the longevity of patients with advanced disease, they do not effectively cross the blood-brain barrier (BBB).¹

Surgery or radiosurgery (SRS) are important modalities for patients with a single brain metastasis, particularly when favorable prognostic factors and systemic disease control are present. However, more than 70% of patients with brain metastases have multiple lesions at the time of presentation which are not considered to be surgically resectable.³ Radiation therapy, either as SRS, fractionated stereotactic radiotherapy (FSRT) or whole brain radiotherapy (WBRT) remains the standard of care for treatment of these patients with unresectable brain metastases (NCCN Clinical Practice Guidelines in Oncology, version 2.2013).

FSRT remains an attractive therapeutic strategy for large brain metastases (>2cm diameter) and/or for those located in eloquent critical locations in the brain. SRS for the treatment of these lesions may lead to an unacceptable rate of late toxicity including brain necrosis.⁴ Fractionating the radiotherapy allows one to deliver a total dose close to that used in SRS while allowing for a decrease in normal tissue injury. However, this treatment modality is not optimal and response rate ranges from 60-80% for FSRT are seen.^{5,6} Radiosensitization may help improve the control of brain metastases treated with FSRT. This strategy may be particularly helpful for those patients who are less likely to have optimal control with FSRT alone.⁷

2.2 TPI 287

Taxanes have well established anti-cancer properties in wide spectrum of malignancies including breast and lung cancer. First generation taxanes (paclitaxel and docetaxel) are one of the main chemotherapeutic agents for the treatment of breast and non-small cell lung cancers. Although these agents are very effective in treatment of extra-cranial disease, minimum efficacy has been shown with their use for intracranial involvement. The efficacy of first generation taxanes on brain metastases is impacted by their inability to permeate the brain. A major limiting factor for their penetration across the BBB is the active efflux back into the circulation by the overexpression of the multidrug-resistant gene product 1 (MDR1) or P-glycoprotein (P-gp).⁸

TPI 287, a new member of taxanes diterpenoid (taxoid) family, is a microtubule-inhibitor with significant cytotoxic activity and brain permeability.⁹ TPI 287 has shown comparable (within 2-fold) or increased cytotoxicity/growth inhibition compared to standard chemotherapeutic agents in human cell lines derived from the following tumors: breast (including a brain metastatic breast cancer cell line), lung, squamous cell carcinoma, pancreas, hepatocellular, colon, uterine, ovarian, prostate, Burkitt's lymphoma, head/neck, neuroblastoma, glioblastoma, and medulloblastoma (Investigator's brochure). TPI 287 was shown to be active (TGI > 58%) in mouse xenograft models of the following human tumors: breast adenocarcinoma, colon adenocarcinoma, prostate adenocarcinoma, pancreatic adenocarcinoma, head/neck tumor, glioblastoma, and ovarian tumor (Investigator's brochure). Moreover, activity exceeding that of the comparator chemotherapeutic agent has been observed in multiple MDR+ tumor models, including breast, colon, head/neck, and neuroblastoma (Investigator's brochure).

TPI 287 has been investigated in 2 phase 1 clinical trials. The initial phase 1 clinical trial used the once weekly for 3 weeks with the fourth week off treatment schedule in subjects with recurrent or refractory cancers. In this study, 48 patients were enrolled and the MTD of weekly TPI 287 was determined to be 127.5 mg/m². Another phase I trial of single agent TPI 287, investigated once every 3 week treatment schedule in 21 patients. In this schedule MTD was 160 mg/m². Overall, the most frequent adverse events (\geq 10%) considered possibly, probably, or definitely related to TPI 287 were peripheral neuropathy (48%), anemia (38%), diarrhea (29%), neuropenia and nausea (24%), fatigue and myalgia (19%), vomiting, asthenia, pyrexia, neuropathy, and alopecia (14%), and leukopenia, thrombocytopenia, abdominal pain, constipation, anorexia, back pain, bone pain, pain in extremity, hypoesthesia, and flushing (10%) (Investigator's brochure).

TPI 287 is a poor substrate for P-gp efflux pump resulting in high brain-to-plasma ratios in the animal models. Brain-to-plasma ratio of this agent after a single injection were as high as 63.8 in the rat and 14.1 in the mouse. Moreover, when used in preclinical model of brain metastasis from breast cancer, TPI 287 resulted in 55% reduction in the formation of large brain metastasis from breast cancer.⁹ Hence, this agent rises as a promising compound for treatment of patients with brain metastasis from primary tumors such as breast and non-small cell lung cancer which are deemed taxane-sensitive.

2.3 Concurrent Radiotherapy with TPI 287

First generation taxanes are potent radiosensitizers and have been widely used as radiosensitizers in various tumors.^{10,11} Preclinical data have shown that taxanes can enhance radiation sensitivity through two major mechanisms: reoxygenation of radioresistant hypoxic cells and cell arrest in in the radiosensitive G2/M phase of the cell cycle.¹² In vivo studies have shown that taxanes can strongly enhance tumor radioresponse, producing enhancement factors of 1.2 to more than 2.0. ¹². Concurrent use of docetaxel and paclitaxel with radiation therapy has shown to be feasible and clinically beneficial in treatment of wide range of malignancies including non-small cell lung cancer, nasopharyngeal cancer, esophageal squamous cell cancer, bladder cancer, and gynecologic cancers.¹³⁻²⁰ RTOG-9705 trial has studied the use of postoperative adjuvant paclitaxel/carboplatin concurrent with thoracic radiotherapy in resected stage II and IIIA nonsmall cell lung cancer.²¹ This phase II trial showed that concurrent use of paclitaxel/carboplatin with radiation therapy to lung is safe and increases progression free survival and overall survival in this group of patients.²¹ Similar results have been demonstrated in another phase II trial by Feigenberg et al.²² Based on these trials concurrent thoracic radiotherapy with paclitaxel/carboplatin has been recommended by NCCN guidelines (version 4.2014) for treatment of resected stage II and IIIA non-small cell lung cancer.

Concurrent chemoradiotherapy to brain has been shown to be feasible and safe and has been established as standard of care for treatment of primary brain tumors such as glioblastoma.²³ However, this potential treatment strategy has not been well developed for metastatic brain disease.

Given the failure rate of FSRT in treating brain metastasis, concurrent chemoradiotherapy could be a potential treatment strategy to overcome resistance to radiotherapy alone. However, brain tissue penetrance has been the limiting factor for the use of taxanes in this setting. With current evidence showing promising data on brain concentration of TPI 287, it would be of great interest to investigate radiosensitizing effect of this agent when used concurrently with radiation therapy for metastatic brain lesions.

2.4 Rationale

In summary brain metastases are grave and challenging complication in patients with metastatic breast and NSCL cancer and result in limited survival. TPI 287 possesses a favorable efficacy and pharmacokinetic profile in pre-clinical models. TPI 287 has been observed preclinically to cross the blood-brain barrier and reach a notable concentration in brain tissue and cerebrospinal fluid.⁹ Furthermore, the use of TPI 287 has resulted in reduction of brain metastasis formation in animal models of breast cancer.⁹

Based on available safety pharmacology, toxicology and pharmacokinetic data from phase 1 study of TPI 287, it can be concluded that TPI 287 has been adequately characterized to support the initiation of this phase 1 trial in combination with radiation in patients with metastatic brain lesions from breast and NSCL cancers.

If the combination is tolerable, further studies of efficacy will be warranted to assess whether the

addition of TPI 287 can potentially increase tumor response, maintain neurologic function, improve quality of life, and extend survival.

2.5 Correlative Studies Background

Pharmacokinetic data in animal models indicate that TPI 287 crosses the blood brain barrier and reaches the brain tissue and cerebrospinal fluid (CSF).⁹ However, the permeability of this compound through blood-brain barrier has not been investigated in human studies.

3. PATIENT SELECTION

3.1 Eligibility Criteria

- Patients must have histologically or cytologically confirmed non-central nervous system primary breast or non-small cell lung cancer.
- Patients must have pathologically or radiologically confirmed metastatic disease in the brain.
- Patients with up to 3 brain metastases (symptomatic and non-symptomatic) can be treated on this study. Maximum diameter of each brain lesion should be ≤ 5 cm. Maximum tumor volume ≤ 120 cc
- Age ≥ 18 years.
- ECOG performance status ≤ 2 (Karnofsky $\geq 60\%$, see Appendix A).
- Life expectancy of greater than 12 weeks.
- Patients requiring treatment with corticosteroids are eligible.
- Treatment with non-enzyme inducing anti-seizure medications is allowed.
- Patients must have normal organ and marrow function as defined below:
 - leukocytes ≥3,000/mcL
 - absolute neutrophil count \geq 1,500/mcL
 - platelets $\geq 100,000/mcL$
 - total bilirubin within normal institutional limits
 - AS T(SGOT)/ALT (SGPT) ≤2.5 × institutional upper limit of normal
 - creatinine within normal institutional limits OR
 - calculated creatinine clearance $\geq 60 \text{ mL/min}/1.73 \text{ m}^2$ for patients with creatinine levels above institutional normal.
- Systemic chemotherapy washout period ≥ 7 days. For investigational dugs and monoclonal antibodies washout period $\geq 5x$ drug half-life. There are no limitations on

number of prior treatment regimens.

- The effects of TPI 287on the developing human fetus is unknown. For this reason, women of child-bearing potential and men must agree to use adequate contraception (hormonal or barrier method of birth control; abstinence) prior to study entry and for the duration of study participation. Should a woman become pregnant or suspect she is pregnant while she or her partner is participating in this study, she should inform her treating physician immediately. Men treated or enrolled on this protocol must also agree to use adequate contraception prior to the study, for the duration of study participation, and 4 months after completion of TPI 287 administration.
- Prior brain surgery or radiation is allowed as long as the metastatic lesion(s) to be targeted in this study has not previously been treated with radiation.
- Ability to understand and the willingness to sign a written informed consent document.

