3.2 Exclusion Criteria

- Patients who have had chemotherapy within 1 week (6 weeks for nitrosoureas or mitomycin C) or investigational therapies/monoclonal antibodies within 5 half-life of investigational compound or those who have not recovered from adverse events due to agents administered more than 1 week earlier. Bisphosphonates, endocrine therapy, and trastuzumab are permitted without restriction.
- Patients who are receiving any other investigational agents.
- Previous treatment of the target lesions with radiation therapy.
- Patients who have previously been treated with whole brain radiation.
- History of allergic reactions attributed to compounds of similar chemical or biologic composition to TPI 287.
- Pregnant women are excluded from this study because TPI 287 is an agent with an unknown but potential risk for teratogenic or abortifacient effects. Because there is an unknown but potential risk for adverse events in nursing infants secondary to treatment of the mother with TPI 287, breastfeeding should be discontinued if the mother is treated with TPI 287.
- Known contraindication to enhanced MRI and CT scan.

 Uncontrolled intercurrent illness including, but not limited to, ongoing or active infection, symptomatic congestive heart failure, unstable angina pectoris, cardiac arrhythmia, uncontrolled seizure activity or psychiatric illness/social situations that would limit compliance with study requirements.

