Number of Patients with DLT at a Given Dose Level	Escalation Decision Rule
0 out of 3	Enter 3 patients at the next dose level.
≥2	Dose escalation will be stopped. This dose level will be declared the maximally administered dose (highest dose administered). Three (3) additional patients will be entered at the next lowest dose level if only 3 patients were treated previously at that dose.
1 out of 3 or ≥ 2 grade 2 CNS toxicities	 Enter at least 3 more patients at this dose level. If 0 of these 3 patients experience DLT, proceed to the next dose level. If 1 or more of this group suffer DLT, then dose escalation is stopped, and this dose is declared the maximally administered dose. Three (3) additional patients will be entered at the next lowest dose level if only 3 patients were treated previously at that dose.
≤1 out of 6 at highest dose level below the maximally administered dose	This is the dose to be used in the expanded cohort and will be considered recommended phase 2 dose. At least 6 patients must be entered at this dose.

Table 2. Dose Escalation Rules

If dose level 1 is found to cause unacceptable toxicity, the dose will be de-escalated to level -1 (7 mg/m^2). Three patients will be enrolled at dose level -1. If no DLT is observed, three additional patients will be enrolled at dose level -1 such that safety is established in at least 6 patients prior to entering dose expansion phase.

Any delayed CNS-toxicity arising within the radiation field but seen beyond the window for DLT registration (> 8weeks following completion of FSRT) will be recorded. Furthermore, occurrence of any delayed-onset treatment related grade 3 or higher central nervous toxicity at any time (during and after DLT period of 8 weeks) will lead to holding dose-escalation and adding 3 patients to the dose level at which toxicity has occurred. Occurrence of additional delayed-onset treatment related grade 3 or higher CNS- toxicity will be reviewed with Protocol Monitoring Committee and IRB to determine whether discontinuation or modification of trial is subsequently warranted.

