5.5 General Concomitant Medication and Supportive Care Guidelines

Because there is a potential for interaction of TPI 287 with other concomitantly administered drugs through the cytochrome P450 system, the use of drugs or herbal supplements that are known to be strong inhibitors/inducers of CYP3A4 and CYP2C8 are not permitted (Appendix B).

Prophylactic use of corticosteroids is allowed during the study to limit symptoms from metastases or radiation.

Non-enzyme inducing anti-epileptic drugs may be utilized to control or prevent seizures.

Principal Investigator should be alerted if the patient is taking any agent known to affect or with the potential to affect selected CYP450 isoenzymes.

5.6 **Duration of Therapy**

Patients will receive TPI 287 on days 1, 8, and 15 (total of 3 doses). On day 1, the TPI 287 will be administered 4 (+/-2) hours prior to FSRT.

5.7 **Duration of Follow Up**

Patients will be seen in follow-up on the 3rd, 6th, 9th, 12th, 15th, and 18th month following the first day of treatment with TPI 287. Patients will be followed for 18 months after first treatment on study or until death, whichever occurs first.

The following will be obtained at pre-treatment evaluation and at each follow up visit: Symptoms history, vital signs/ height and weight, physical examination, KPS/ECOG score, Mini-Mental State Examination, steroid use, quality of life questionnaire, and toxicity evaluation.

Radiologic assessment, MRI brain with and without gadolinium, will be performed at pretreatment and every three months following the end of treatment until the patient is off-study or reaches the 18 month study completion date.

Furthermore, the principal investigator will have close collaboration with oncologists treating the systemic malignancy. Information regarding the status of systemic malignancy such as results of standard imaging evaluations, serum biomarkers measurements, and systemic treatments will be collected and recorded at each visit.

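### Section 3.1 sets a 4-month post-dose contraception minimum for men but none for women of child-bearing potential, so a woman who leaves all follow-up early has agreed to a shorter period.

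*Combined protocol and SAP*

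**What the plan says.** The rule is an eligibility criterion in protocol Section 3.1, so it is an agreement made at entry. It has two parts.

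- Both sexes: "women of child-bearing potential and men must agree to use adequate contraception". The stated methods are hormonal, barrier or "abstinence) prior to study entry and for the duration of study participation".
- Men only: "Men treated or enrolled on this protocol must also agree to use adequate contraception prior to the study", and then "for the duration of study participation, and 4 months after completion of TPI 287 administration".

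The reason is fetal risk. Section 3.1 says the effect on the fetus is not known, and Section 3.2 says "Pregnant women are excluded from this study because TPI 287 is an agent with an unknown but potential risk for teratogenic or abortifacient effects".

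How long participation lasts comes from other sections. Section 5.7 says "Patients will be followed for 18 months after first treatment on study or until death, whichever occurs first", with patients "seen in follow-up on the 3rd, 6th, 9th, 12th, 15th, and 18th month following the first day of treatment". Section 5.8 lets patients withdraw whenever they choose, and keeps following discontinued patients for progression. Note g of the Section 10 calendar has disease status and adverse events collected about every 12 weeks after the final visit.

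**The concern.** Women's cover ends when participation ends, while men's cannot end sooner than 4 months after the last dose. Fetal exposure risk depends on when the drug was last given, not on when the patient leaves the study. The woman who received the drug is also the person in whom a fetus would be directly exposed, yet she is the one without a minimum. The protocol gives no reason for the difference.

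The end of participation is itself not defined for someone removed under Section 5.8 but still followed. Section 5.7 recognises that a patient can be off study before 18 months, and Section 7.4 ends adverse event reporting on the last day of participation, but neither says which date that is for such a patient.

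At stake is possible fetal exposure in a woman who leaves early. The MTD, the endpoints and the analyses do not depend on this rule.

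**Working it through.** **Is there a post-dose period for women elsewhere?** The candidate sections are:

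- Section 5.8: pregnancy is a reason for removal; no contraception period.
- Section 7.5: pregnancies on study or within 30 days after treatment stops are reported; this is a reporting window.
- Section 7.7: covers pregnancy while on TPI 287; no period after dosing.
- Section 10: one B-HCG test at baseline; no contraception period.

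None supplies the missing minimum.

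**Inputs.** Doses on days 1, 8 and 15 (Section 5.6), so the last planned dose is 14 days after the first. Men's minimum is 4 months after the last dose (Section 3.1). Follow-up is 18 months from first treatment, with visits every 3 months (Section 5.7). The final visit is about 30 days after the last treatment, with contacts about every 12 weeks after it (Section 10, notes f and g). I take one month as 365.25 / 12 = 30.44 days.

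**Men's minimum in days.** 4 × 30.44 = 121.8 days after the last dose.

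**A woman who stays to the end.** 18 × 30.44 = 547.9 days from first dose; 547.9 − 14 = 533.9 days, or 17.5 months, after the last dose. Her period is far longer than the men's minimum.

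**Latest exit that leaves her below it.** Days from first dose = (days from first to last dose) + 121.8.

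| Dosing | Last dose, days after first | Threshold, days | Months |
|---|---|---|---|
| Day 1 only | 0 | 121.8 | 4.0 |
| Days 1 and 8 | 7 | 128.8 | 4.2 |
| All three, on schedule | 14 | 135.8 | 4.5 |
| All three, one 2-week delay | 28 | 149.8 | 4.9 |
| All three, two 2-week delays | 42 | 163.8 | 5.4 |

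The delay rows use the roughly 2-week limit in the Section 6 tables. Even the longest case closes before the month 6 visit, at 6 × 30.44 = 182.6 days.

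**Her agreed period after a day 15 last dose, by point of full withdrawal.**

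| Point of withdrawal | Days after last dose | Against men's 121.8 |
|---|---|---|
| Final visit | 30 | 92 shorter |
| Month 3 visit | 91.3 − 14 = 77.3 | 44 shorter |
| First 12-week contact after final visit | 30 + 84 = 114 | 8 shorter |
| Month 6 visit | 182.6 − 14 = 168.6 | longer |

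These are scenarios, not forecasts. Visit times are approximate, so the 8-day difference has no practical meaning.

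**Ceiling on patients.** Section 14.2 caps escalation at 36 and sets 10 in total at the expansion dose, counting those already treated there. Table 2 in Section 5.4 says of that dose: "At least 6 patients must be entered at this dose". So at most 36 + (10 − 6) = 40 patients are treated, before replacements. How many are women of child-bearing potential who leave all follow-up early cannot be derived.

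**The case against.** The strongest reply is that participation already gives women a longer period than men's minimum. A woman who stays is covered for about 17.5 months after her last planned dose, and discontinued patients remain in follow-up. This stands, and it confines the clear gap to full early withdrawal. Women removed under Section 5.8 are affected only if participation is read as ending at removal.

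The second reply is that the men's 4 months is unexplained and may not suit women. This also stands. The documents give neither its basis nor the period women need, so the day counts measure distance from the protocol's own figure and do not show a shortfall in protection. They still leave an early-leaving woman with no minimum at all after dosing.

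The third is that the consent form may give the advice. Those pages are not in this copy, so the point concerns the protocol text only.

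The last is that other safeguards lower the stakes: the baseline pregnancy test, exclusion of pregnant women, the duty to tell the treating physician of a pregnancy at once, and the reporting rules. They help, but they screen at entry or act once a pregnancy has occurred or is suspected. None asks a woman to keep using contraception after she leaves.

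**Conclusion.** The concern holds, with narrow reach. As written, a dosed woman of child-bearing potential who withdraws from all follow-up within about 4.5 months of first dose has agreed to a shorter period than a man leaving on the same day, by up to about 92 days if she leaves at the final visit or later. The threshold assumes three doses on schedule; it ranges from 4.0 months (one dose) to 5.4 months (two 2-week delays). It also assumes that continued follow-up counts as participation; on a narrower reading, women removed under Section 5.8 are exposed too. The text should be changed because the stated risk is to a fetus and the change is simple. My confidence is moderate, because the right period for women and the content of the consent form cannot be checked here.

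**What to change.** Amend Section 3.1 so that women of child-bearing potential, like men, agree to contraception until the later of the end of study participation or at least 4 months after the last TPI 287 dose, whether or not they leave early. Use a longer period if the Investigator's Brochure supports one. Keep the participation clause, so that no one's present cover is shortened. Bring the consent form into line if it does not already say this.

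The cost is a short amendment and a longer commitment for women who leave early. There are no added visits or tests, and no effect on the MTD or the analyses. As an optional consistency edit, the pregnancy reporting in Sections 7.5 and 7.7 could be aligned to the same period.
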